### 3.6. Dose Escalation

Doses will be administered in an escalating manner following satisfactory review by the PSRT of the safety, tolerability, and PK data (up to 5 days postdose) from the lower dose levels. Any clinically significant results will be discussed before dose escalation continues. Interim PK data will also be reviewed in terms of dose escalation and to confirm that the study design remains appropriate. Doses may be reduced and may be lower than the starting dose. There will be a minimum of 7 days between completion of Day 6 assessments in the previous dose group and dosing in the next dose group to allow sufficient time for an adequate safety review.

Dose escalation will only occur if data from all participants in the dosing group have been reviewed by the PSRT.

An interim safety report, summarizing results from all available safety assessments, will be sent to the Sponsor prior to the start of each successive group.

### **3.7. Dose Escalation Stopping Rules**

Following discussion among the PSRT, dose escalation will stop if:

- Clinically relevant signs or symptoms of similar nature occur in 2 or more subjects in a group that, in the opinion of the Investigator, warrant stopping of dose escalation.
- One or more subjects experience a serious AE (SAE) that is considered to be related to IMP.
- Two or more subjects experience a Grade 3 or 4 AE or laboratory abnormality that is considered to be at least possibly related to IMP.
- There is evidence of clinically significant increases in liver function tests (aspartate aminotransferase, alanine aminotransferase, alkaline phosphatase, bilirubin, and/or gamma-glutamyl transferase), defined as 3 times the upper limit of normal in 3 or more subjects in a group (confirmed with repeat testing).
- Clinically significant increases in serum creatinine or blood urea nitrogen, defined as 1.5 times and 2 times the upper limit of normal, respectively (confirmed with repeat testing), in 3 or more subjects in a group.

### **3.8. Overall Study Stopping Rules**

The study may be discontinued at the discretion of the PSRT if any of the following criteria are met:

- AEs unknown to date (i.e., not previously reported in any similar investigational study drug trial with respect to their nature, severity, and/or duration)
- increased frequency, severity, and/or duration of known, anticipated, or previously reported AEs (this may also apply to AEs defined at Day -1 as baseline signs and symptoms)
- medical or ethical reasons affecting the continued performance of the study
- difficulties in the recruitment of subjects
- cancelation of drug development.

The study will be discontinued if 2 or more subjects experience a Grade 3 or 4 AE or laboratory abnormality that is considered to be at least possibly related to IMP.

The study may be stopped at any time prior to completion by the sponsor, FDA, IRB, and/or doctors participating in the study.

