### 3.4.1. Dose Interval

Dosing at each dose level will be such that 2 subjects (1 CPT31 and 1 placebo) will be dosed 72 hours before the remaining 6 subjects. After dosing the first 2 subjects on a separate day, a minimum of a 5-minute dosing interval for the remaining 6 subjects in each dose-ascending cohort is considered acceptable. Continuation to dose the remaining 6 subjects will be made by the PSRT.

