## 5.4. Blinding

The following controls will be employed to maintain the double-blind status of the study:

- The placebo solution may not be identical in appearance to the CPT31 solution. The unblinded pharmacy staff member will prepare syringes for injection (placebo and CPT31 solution) and an unblinded study nurse will perform the injections. If color differences are apparent between active and placebo in dosing syringes, then subjects will be blindfolded prior to and during study drug/placebo injection. Other Covance staff, e.g., CRCs, will be asked to avert their eyes during study drug/placebo injection.

- The Investigator and other members of staff involved with the study will remain blinded to the treatment randomization code during the assembly procedure.
- Interim bioanalytical data will be provided to the PSRT in a blinded manner.

To maintain the blind, the Investigator will be provided with a sealed randomization code for each subject, containing details of their treatment. These individual sealed envelopes will be kept in a limited access area that is accessible 24 hours a day. In order to manage subject safety or to support dose escalation decisions (in the event of possibly treatment-related SAEs or Grade  $\geq 3$  AEs), the decision to unblind resides solely with the Investigator. Whenever possible and providing it does not interfere with or delay any decision in the best interest of the subject, the Investigator will discuss the intended code-break with the Sponsor. If it becomes necessary to break the code during the study, the date, time, and reason will be recorded in the subject's source data and on the individual envelope and will be witnessed by a second person.

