### Relationship to Study Treatment

The Investigator (or designee) will make a determination of the relationship of the AE to the study drug using a 4-category system according to the following guidelines:

- **Not Related:** The AE is definitely caused by the subject's clinical state or the study procedure/conditions.
- **Unlikely Related:** The temporal association between the AE and the drug is such that the drug is not likely to have any reasonable association with the AE.
- **Possibly Related:** The AE follows a reasonable temporal sequence from the time of drug administration but could have been produced by the subject's clinical state or the study procedures/conditions.

- **Related:** The AE follows a reasonable temporal sequence from administration of the drug, abates upon discontinuation of the drug, follows a known or hypothesized cause-effect relationship, and (if appropriate) reappears when the drug is reintroduced.

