### **Follow-up of Adverse Events**

Every reasonable effort will be made to follow up with subjects who have AEs. Any subject who has an ongoing AE that is possibly related or related to the IMP or study procedures at the Follow-up visit will be followed up, where possible, until resolution or until the unresolved AE is judged by the Investigator (or designee) to have stabilized. This will be completed at the Investigator's (or designee's) discretion. Any subject who has an ongoing AE that is not related or unlikely related to the IMP or study procedures at the Follow-up visit can be closed out as ongoing at the Investigator's discretion.

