### **Adverse Drug Reactions**

All noxious and unintended responses to an IMP (i.e., where a causal relationship between an IMP and an AE is at least a reasonable possibility) related to any dose should be considered as adverse drug reactions.

For marketed medicinal products, a response to a drug which is noxious and unintended, and which occurs at doses normally used in man for prophylaxis, diagnosis, or therapy of diseases or for modification of physiological function is to be considered an adverse drug reaction.

An unexpected adverse drug reaction is defined as an adverse reaction, the nature or severity of which is not consistent with the applicable product information (e.g., Investigator's Brochure for an unapproved IMP).

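### The graded stopping rules in Protocol 3.7 and 3.8 omit Grade 5 (death); secondarily, the 3.7 SAE rule uses a narrower causality test than the bullet that follows it

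*Protocol*

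**What the plan says.** Section 3.7 lists the conditions that stop dose escalation. Two of them matter here:

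- SAE bullet: "One or more subjects experience a serious AE (SAE) that is considered to be related to IMP".
- Graded bullet: "Two or more subjects experience a Grade 3 or 4 AE or laboratory abnormality that is considered to be at least possibly related to IMP".

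Section 3.8 repeats the graded condition as the only compulsory ground for ending the study: "The study will be discontinued if 2 or more subjects experience a Grade 3 or 4 AE or laboratory abnormality", again with causality at least possible. Its other grounds are discretionary.

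Three other parts of the protocol define or use the same terms:

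- **Severity.** Appendix 1 has five grades, and Grade 5 is death. Section 5.4 allows code-breaking to support escalation decisions "in the event of possibly treatment-related SAEs or Grade" 3 and above, so its grade range is open at the top.
- **Causality.** Appendix 1 has four categories. Possibly Related is separate from Related and is defined as: "The AE follows a reasonable temporal sequence from the time of drug administration but could have been produced by" the subject's condition or the study procedures.
- **Usage.** Where Appendix 1 means both categories it says so, as in its follow-up rule for any "ongoing AE that is possibly related or related to the IMP or study procedures". It defines a drug reaction as a case "where a causal relationship between an IMP and an AE is at least a reasonable possibility". SAP 8.6.1 also counts possibly related events as treatment-related.

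**The concern.** Stopping rules fix the response before anyone has seen the event. With Grade 5 left out, the written rules rank severity in the wrong order: two possibly related laboratory values compel discontinuation, and two possibly related deaths do not.

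The SAE bullet would normally catch a death, since a fatal event is an SAE. However, it asks for Related, while the next bullet accepts at least possibly related. A possibly related death therefore falls between the two.

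This is a first-in-human study. The 97-fold rat margin in Table 2 applies to the starting dose. At the planned top dose it is 0.97/0.24, about 4-fold. The protocol also allows doses above that level and up to three additional groups.

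**Working it through.** The documents give no operating characteristics for these rules, so there is no figure to reproduce. The check has three steps.

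**1. Apply the literal rules to serious events.** The inputs are the SAE and graded bullets of 3.7 and the compulsory rule of 3.8. The cells are 4 severities × 2 causality categories × 1 or 2 subjects = 16.

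| Serious event | Possibly related, 1 subject | Possibly related, 2 subjects | Related, 1 subject | Related, 2 subjects |
|---|---|---|---|---|
| Grade 2 or lower | none | none | escalation stop | escalation stop |
| Grade 3 | none | discontinue | escalation stop | discontinue |
| Grade 4 | none | discontinue | escalation stop | discontinue |
| Grade 5 | none | none | escalation stop | escalation stop |

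Totals: 6 cells with no compulsory rule, 6 with an escalation stop only, 4 with discontinuation. All 6 empty cells are possibly related. The 4 fatal cells split 2 / 2 / 0.

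Writing Grade 3 or higher, and adding a dosing halt at one at-least-possibly-related death, moves all 4 fatal cells to a halt or discontinuation. The table becomes 4 / 4 / 8. The 4 cells still empty are nonfatal and possibly related: one subject at each of the three nonfatal severities, and two subjects at Grade 2 or lower. Those are what the causality wording of the SAE bullet governs.

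The count leaves out the judgement-based and organ-specific laboratory bullets of 3.7, the discretionary stops in 3.8, and any Grade 3 or 4 event recorded separately before a death. The cells are unweighted. They show what the rules cover, not how likely the events are.

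**2. Mixed pairs.** For two subjects, each with an at-least-possibly-related event of Grade 3, 4 or 5, there are six pairs. The present wording counts 3+3, 3+4 and 4+4. It misses 3+5, 4+5 and 5+5. Grade 3 or higher counts all six.

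**3. Cost of widening the SAE bullet.** Three of the five bullets in 3.7 are limited to a group. The SAE and graded bullets are not, so read literally they accumulate across groups. Escalation decisions within the planned doses follow A1, A2 and A3, giving n = 3 × 8 = 24. Placebo subjects are included because causality is judged blind. Let p be the per-subject chance of a possibly related SAE. The documents give no value, so 1% and 5% are assumed.

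- One-subject trigger: P(≥1) = 1 − (1 − p)^24. At 1%: 1 − 0.7857 = 21.4%. At 5%: 1 − 0.2920 = 70.8%.
- Present two-subject trigger, if all these SAEs are Grade 3 or 4: P(≥2) = 1 − (1 − p)^24 − 24p(1 − p)^23. At 1%: 1 − 0.7857 − 0.1905 = 2.4%. At 5%: 1 − 0.2920 − 0.3688 = 33.9%.

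If these SAEs were all Grade 2 or lower, the present SAE and graded bullets would not be triggered at all. For a single group of 8, the one-subject trigger gives 7.7% and 33.7%, which understates the cumulative effect.

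**The case against.** The strongest reply is that these rules are not the main barrier. Section 3.6 makes escalation depend on satisfactory PSRT review, with clinically significant results discussed first. Section 3.7 itself operates after PSRT discussion. Section 3.8 lets the PSRT stop on broad grounds, and the sponsor, FDA, IRB or study doctors may stop at any time. Appendix 1 sends potentially FDA-reportable events to the PSRT within 24 hours. This stands. A reader might infer that a possibly related death would pass unnoticed, or that dosing would go on by default. The documents do not support that.

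Some of the gap remains. The review in 3.6 covers data to 5 days after dosing, and the next group may be dosed 7 days after Day 6 assessments, whereas Follow-up is at 28 to 30 days. A late event can therefore arise after the gate has been passed, and then only discretion applies.

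On causality, the SAE bullet can be read as a deliberate two-tier design: one subject with firmer attribution, or two with weaker attribution, with unblinding under 5.4 to settle doubtful cases. That is defensible, and it argues against an automatic permanent stop. It does not explain the absence of Grade 5.

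Three stronger readings should be set aside:

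- That possibly related SAEs are left out altogether. Those of Grade 3 or 4 count in both graded rules once two subjects are affected.
- That nothing holds the other six subjects after a sentinel SAE. Section 5.3 makes their dosing conditional on no safety concern, and 3.4.1 says: "Continuation to dose the remaining 6 subjects will be made by the PSRT".
- That no death could be called Related, because that definition mentions abatement when the drug is stopped. Appendix 1 presents the definitions as guidelines for the investigator's judgement, so the category is not closed to a fatal event.

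**Conclusion.** The Grade 5 omission holds on the text and should be corrected. It leaves 2 of the 4 fatal cells with no compulsory SAE- or grade-based rule and the other 2 with an escalation stop only, and it misses 3 of the 6 grade pairs.

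The causality mismatch is real but secondary. A single possibly related SAE triggers no compulsory stop, and Grade 3 or 4 SAEs in this category count only at two subjects. The reading rests on the separate Appendix 1 categories and on the contrast between adjacent bullets. A looser use of related is possible but less likely.

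The practical consequence is limited by PSRT control of escalation and of second-cohort dosing, and by the discretionary stops. What is missing is a response fixed in advance. The stopping probabilities depend on assumed rates, independence between subjects and a cumulative count over A1 to A3.

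**What to change.** 1. In both 3.7 and 3.8, replace Grade 3 or 4 with *Grade 3 or higher*.
2. Add to 3.8: *Any death considered at least possibly related to IMP halts all dosing pending PSRT review.*
3. In the 3.7 SAE bullet, use *at least possibly related*. State that for an SAE judged only possibly related, escalation is paused and may resume after a documented PSRT decision, with unblinding under 5.4 if needed. Limiting the resume clause in this way keeps the present stop for related SAEs.

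No further sentinel rule is needed, since 3.4.1 and 5.3 already gate the second cohort.

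The cost is a protocol amendment with IRB and Division of AIDS approval (Appendix 5), and no new data, procedures or subjects. Changes 1 and 2 should cost almost nothing in operation. Change 3 will produce more pauses. Over A1 to A3 the chance of at least one is 21.4% or 70.8% at the assumed rates, which is why the pause must be reversible.

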## **4. SELECTION OF STUDY POPULATION**

### **4.1. Healthy Subjects**

#### **4.1.1. Inclusion Criteria**

Subjects must satisfy all the following criteria at the Screening Visit unless otherwise stated:

1. Males or females, of any race, between 18 and 55 years of age, inclusive.
2. Body mass index between 18.0 and 32.0 kg/m^2, inclusive.
3. In good health, determined by no clinically significant findings from medical and surgical history, physical examination, 12-lead ECG, vital signs measurements, and clinical laboratory evaluations (congenital nonhemolytic hyperbilirubinemia [e.g., suspicion of Gilbert's syndrome based on total and direct bilirubin] is not acceptable) at Screening and/or Day -1 as assessed by the Investigator (or designee).
4. Females will not be pregnant or have been within the previous 3 months, or lactating, and females of childbearing potential and males will agree to use contraception, as detailed in [Appendix 4](#).
5. Able to comprehend and willing to sign an ICF and to abide by the study restrictions.

#### **4.1.2. Exclusion Criteria**

Subjects will be excluded from the study if they satisfy any of the following criteria at the Screening Visit unless otherwise stated:

1. Significant history or clinical manifestation of any metabolic, allergic, dermatological, hepatic, renal, hematological, pulmonary, cardiovascular, gastrointestinal, neurological, respiratory, endocrine, or psychiatric disorder, as determined by the Investigator (or designee).
2. A  $\geq$ Grade 2 laboratory abnormality at Screening or Day -1 as defined by the Division of AIDS Table for Grading the Severity of Adult and Pediatric Adverse Events, Version 2.1 dated July 2017.
3. Estimated glomerular filtration rate (eGFR per CKD-Epi equation) of  $<90$  ml/min/1.73 m^2.
4. Known sensitivity to CPT31 or any of its components.
5. History of significant hypersensitivity, intolerance, or allergy to any drug compound, food, or other substance, unless approved by the Investigator (or designee).
6. History of alcoholism or drug/chemical abuse within 2 years prior to Day -1.
7. Alcohol consumption of  $> 21$  units per week for males and  $> 14$  units for females. One unit of alcohol equals 12 oz (360 mL) beer, 1½ oz (45 mL) liquor, or 5 oz (150 mL) wine.
8. Positive urine drug screen at Screening or positive alcohol breath test result or positive urine drug screen on Day -1.
9. Positive HIV test as documented by Combo Ag/Ab HIV-1/HIV-2 immunoassay.
10. Positive hepatitis B surface antigen, positive hepatitis B core antibody with negative hepatitis B surface antibody test result, or positive hepatitis C antibody at Screening or within 3 months before first dose of study treatment.
11. Participation in a clinical study involving administration of an investigational drug in the past 30 days prior to dosing.

12. Use or intend to use any prescription or over the counter medications/products (including HIV medications being used for pre-exposure prophylaxis) other than hormone replacement therapy, oral, implantable, transdermal, injectable, or intrauterine contraceptives or acetaminophen up to 2 grams per day for no more than 3 consecutive days within 14 days prior to dosing, unless deemed acceptable by the Investigator (or designee).
13. Use of tobacco- or nicotine-containing products within 3 months prior to Day -1, or positive cotinine at Screening or Day -1.
14. Receipt of blood products within 2 months prior to Day -1.
15. Donation of blood from 3 months prior to Screening, plasma from 2 weeks prior to Screening, or platelets from 6 weeks prior to Screening.
16. Poor peripheral venous access.
17. Have previously completed or withdrawn from this study or any other study investigating CPT31 and have previously received the investigational product.
18. Subjects who, in the opinion of the Investigator (or designee), should not participate in this study.

#### **4.1.2.1. *Additional Exclusion Criteria***

19. Have any clinically significant abnormal ECG results constituting a risk while taking the investigational product, as determined by the Investigator, such as any of the following, as determined by single 12-lead ECG:
  - a. QT interval corrected for heart rate using Fridericia's method (QTcF) >450 ms for males and >470 ms for females, confirmed by calculating the mean of the original value and 2 repeats.
  - b. QRS duration >120 ms confirmed by calculating the mean of the original value and 2 repeats.
  - c. PR interval >220 ms confirmed by calculating the mean of the original value and 2 repeats.
  - d. findings which would make QTc measurements difficult or QTc data uninterpretable.
  - e. history of additional risk factors for torsades de pointes (e.g., heart failure, hypokalemia, family history of long QT syndrome).
  - f. Risks related to bradycardia, for example, second or third degree atrioventricular block or sick sinus syndrome

#### **4.2. Subject Number and Identification**

Subjects will have a unique identification number used at Screening. Subjects will be assigned a subject number at the time of their randomization. Assignment of subject numbers will be in ascending order and no numbers will be omitted (e.g., Subjects 0101, 0102, etc.). Replacement subjects (Section 4.3) will be assigned a subject number corresponding to the

number of the subject he/she is replacing plus 1000 (e.g., Subject 1101 replaces Subject 0101).

Subjects will be identified by identification or subject number only on all study documentation. A list identifying the subjects by subject number will be kept in the Site Master File. Photos of subjects may be taken for subject identification.

#### **4.3. Subject Withdrawal and Replacement**

A subject is free to withdraw from the study at any time. In addition, a subject will be withdrawn if any of the following criteria are met:

- change in compliance with any inclusion/exclusion criterion that is clinically relevant and affects subject safety as determined by the Investigator (or designee)
- noncompliance with the study restrictions that might affect subject safety or study assessments/objectives, as considered applicable by the Investigator (or designee)
- any clinically relevant sign or symptom that, in the opinion of the Investigator (or designee), warrants subject withdrawal.

If a subject is withdrawn, the Sponsor will be notified and the date and reason(s) for the withdrawal will be documented in the subject's electronic Case Report Form (eCRF). If a subject is withdrawn, efforts will be made to perform all follow-up assessments, if possible ([Appendix 6](#)). Other procedures may be performed at the Investigator's (or designee's) and/or Sponsor's discretion. If the subject is in-house, these procedures should be performed before the subject is discharged from the clinic. The Investigator (or designee) may also request that the subject return for an additional Follow-up visit. All withdrawn subjects will be followed until resolution of all their AEs or until the unresolved AEs are judged by the Investigator (or designee) to have stabilized.

Subjects who are withdrawn for reasons not related to study drug may be replaced following discussion of the PSRT Subjects withdrawn as a result of AEs thought to be related to the study drug will generally not be replaced.

### **5. STUDY TREATMENTS**

#### **5.1. Description, Storage, Packaging, and Labeling**

The IMPs (15 mg/mL CPT31 histidine formulation [50 mM histidine, 200 mM mannitol, pH 7.2 solution for SC injection] and placebo) will be supplied by the Sponsor (or designee), along with the batch/lot numbers and Certificates of Analysis. All IMPs will be provided in single-use vials.

All IMPs will be stored at 2°C to 8°C at the study site in a location that is locked with restricted access.

The IMPs will be labeled in accordance with national laws and regulations.

